4.2 Early study termination

The study can be terminated at any time for any reason by Novartis. Should this be necessary, the patient should be seen as soon as possible and the same assessments should be performed as described in [Section 7.6](#) for a prematurely withdrawn patient. The investigator may be informed of additional procedures to be followed in order to ensure that adequate consideration is given to the protection of the patient's interests. The investigator will be responsible for informing the IRB and/or EC of the early termination of the trial.

5 Population

5.1 Patient population

Adult male or female patients ≥ 18 years of age diagnosed with PMF, PPV MF, or PET-MF who have either received prior treatment with commercially available agents, investigational drug or never received treatment are eligible for this Expanded Access Study.

All relevant medical and other considerations should be taken into account when deciding whether this protocol is appropriate for a particular patient. To maximize patient safety, patients should be treated on this protocol only at centers having ready and adequate staff to care for the thrombocytopenic patient. Physicians should consider the risks and benefits of any therapy and, therefore, only enroll patients for whom the agents administered are appropriate. Although they will not be considered as formal eligibility criteria, as part of this decision-making process physicians should recognize that the following may increase the risk to the patient entering this protocol: physicians should be aware that studies show CYP3A4 is the major human CYP450 isoenzyme catalyzing biotransformation of INC424. A clinical study where a strong CYP3A4 inhibitor (ketoconazole) and INC424 was co-administered resulted in a 90% increase in AUC of INC424. Thus, INC424 dose should be adjusted when co-administration with a strong CYP3A4 inhibitor (see [Section 6.2.4](#)). Other CYP3A4 inhibitors or inducers are to be dosed with caution.

5.2 Inclusion criteria

Patients eligible for inclusion in this study have to meet **all** of the following criteria:

1. Patients must give written informed consent according to local guidelines prior to any screening procedures.
2. Patients must not be eligible for another ongoing INC424 clinical trial.
3. Male or female patients aged ≥ 18 years of age.
4. Patients must be diagnosed with PMF, PPV MF or PET-MF, according to the 2008 revised International Standard Criteria [Appendix I](#), [Swerdlow 2008](#), [Vardiman 2009](#), [Barosi 2008](#)), irrespective of JAK2 mutation status.
5. Patients with PMF requiring therapy must be classified as high risk (3 prognostic factors) OR intermediate risk level 2 (2 prognostic factors, no more), OR intermediate risk level 1 (1 prognostic factor, no more) with an enlarged spleen (assessment to occur at the Screening Visit).

The prognostic factors, defined by the International Working Group ([Cervantes 2009](#)) are:

- Age > 65 years;
- Presence of constitutional symptoms (weight loss, fever, night sweats);
- Marked anemia (Hgb < 10 g/dL)*;
- Leukocytosis (history of WBC $> 25 \times 10^9/L$);
- Circulating blasts $> 1\%$ (in the peripheral blood).

*A Hgb value < 10 g/dL must be demonstrated during the Screening Visit for patients who are not transfusion dependent. Patients receiving regular transfusions of packed

red blood cells will be considered to have Hgb < 10 g/dL for the purpose of evaluation of risk factors.

6. Patients with Intermediate-1 disease and splenomegaly must have a palpable spleen measuring 5 cm or greater from the costal margin to the point of greatest splenic protrusion.
7. Patients must have a peripheral blood blast count percentage of < 10%.
8. Patients with adequate liver function defined as total bilirubin or direct bilirubin $\leq 2.0 \times$ ULN and ALT $\leq 2.5 \times$ ULN.
9. Patients with adequate renal function defined as serum creatinine $\leq 2 \times$ ULN.
10. Patients with an ECOG PS of 0, 1, or 2 ([Appendix IV](#)).
11. Women of childbearing potential must have had a negative serum pregnancy test within 14 days prior to the administration of study drug.
12. Patients must have recovered or stabilized sufficiently from any adverse drug reactions associated with prior treatment before beginning treatment with INC424.
13. Fedratinib pretreated patients with documented complete physical examination including full neurologic examination and cardiology assessment, thiamine level testing, and MRI of the brain if indicated based on signs or symptoms. Patients pretreated with fedratinib should have completed or be receiving thiamine supplementation according to the investigator's instructions.

5.3 Exclusion criteria

Patients eligible for this study must **not** meet any of the following criteria:

1. Patients eligible for hematopoietic stem cell transplantation (suitable candidate and a suitable donor is available).
2. Patients with history of malignancy in past 3 years except for treated, early-stage squamous or basal cell carcinoma in situ.
3. Patients receiving any medication listed in the "Prohibited Medications" listing ([Section 6.3.3](#) and [Appendix VI](#)).
4. Impairment of gastrointestinal (GI) function or GI disease that may significantly alter the absorption of oral INC424 (e.g., ulcerative diseases, uncontrolled nausea, vomiting, diarrhea, malabsorption syndrome, small bowel resection).
5. Patients with cardiac disease which in the investigator's opinion may jeopardize the safety of the patient or the compliance with the protocol.
6. Patients with currently uncontrolled or unstable angina, rapid or paroxysmal atrial fibrillation or recent (approximately 6 months) myocardial infarction or acute coronary syndrome.
7. Patients with clinically significant bacterial, fungal, parasitic or viral infection which require therapy. Patients with acute bacterial infections requiring antibiotic use should delay screening/enrollment until the course of antibiotic therapy has been completed.
8. Patients with known active hepatitis A, B, C or who are HIV-positive.
9. Patients with inadequate bone marrow reserve at the Baseline visit as demonstrated by:
 - ANC $\leq 1000/\mu\text{L}$.

- Platelet count <50,000/ μ L without the assistance of growth factors, thrombopoietic factors or platelet transfusions.

10. Patients with any history of platelet counts < 50,000/ μ L or ANC < 500/ μ L except during treatment for a MPD or treatment with cytotoxic therapy for any other reason.

11. Patients with coagulation parameters (PT, PTT, or INR) >1.5 x ULN.

12. Patients with known hypersensitivity to INC424 or other JAK1/2 inhibitors, or to their excipients.

13. Patients under ongoing treatment with another investigational medication or having been treated with an investigational medication within 30 days of screening or with fedratinib within 14 days of screening.

14. Pregnant or nursing (lactating) women, where pregnancy is defined as the state of a female after conception and until the termination of gestation, confirmed by a positive hCG laboratory test (> 5 mIU/mL).

15. Women of child-bearing potential, defined as all women physiologically capable of becoming pregnant, unless they are using highly effective methods of contraception throughout the study duration inclusive of 28 day safety follow up. Highly effective contraception methods include:

[figure not shown]
- Total abstinence (when this is in line with the preferred and usual lifestyle of the subject). Periodic abstinence (e.g., calendar, ovulation, symptothermal, post-ovulation methods) and withdrawal are not acceptable methods of contraception
- Female sterilization (have had surgical bilateral oophorectomy with or without hysterectomy), total hysterectomy or tubal ligation at least six weeks before taking study treatment. In case of oophorectomy alone, only when the reproductive status of the woman has been confirmed by follow up hormone level assessment
- Male sterilization (at least 6 months prior to screening). The vasectomized male partner should be the sole partner for that subject.
- Use of oral, injected or implanted hormonal methods of contraception or placement of an intrauterine device (IUD) or intrauterine system (IUS) or other forms of hormonal contraception that have comparable efficacy (failure rate <1%), for example hormone vaginal ring or transdermal hormone contraception

Women are considered post-menopausal and not of child bearing potential if they have had 12 months of natural (spontaneous) amenorrhea with an appropriate clinical profile (e.g. age appropriate, history of vasomotor symptoms) or have had surgical bilateral oophorectomy (with or without hysterectomy), total hysterectomy or tubal ligation at least six weeks ago. In the case of oophorectomy alone, only when the reproductive status of the woman has been confirmed by follow up hormone level assessment is she considered not of child bearing potential.

16. Patients who are unable to comprehend or are unwilling to sign an ICF

17. Patients with active alcohol or drug addiction that would interfere with their ability to comply with the study requirements

18. Patients with any concurrent condition that, in the Investigator's opinion would jeopardize the safety of the patient or compliance with the protocol.

19. In the case of ruxolitinib pretreated patients, ruxolitinib primary resistant patients defined as:

- No spleen reduction within the first 12 weeks after front line therapy with ruxolitinib. AND
- No reduction in symptoms within the first 12 weeks after first-line treatment with ruxolitinib.

20. In the case of ruxolitinib pretreated patients, patients discontinuing ruxolitinib due to a Grade 4 AE related or suspected to be related to ruxolitinib.

6 Treatment

6.1 Investigational treatment, other study treatment, supportive treatment

6.1.1 Study drug dosing

All eligible patients with PMF, PPV MF, or PET MF who consent to participate in this study will receive INC424 open-label investigational drug provided free of charge by Novartis Pharmaceuticals at a dose of 5 – 25 mg BID [dose based on Baseline platelet count] until either:

[figure not shown]
- Disease progression;
- Transplant;
- Unacceptable toxicity;
- Death;
- Discontinuation from the study for any other reason;
- Physician decision
- Withdrawal of informed consent;
- Until 24-months after LPFV; or
- Until the drug is commercially available, whichever occurs first.

The starting dose of INC424 will be determined based on baseline platelet counts as follows:

- Patients with a baseline platelet count of > 200,000/ μ L will begin dosing at 20 mg PO BID.
- Patients with a baseline platelet count of between 100,000/ μ L – 200,000/ μ L (inclusive) will begin dosing at 15 mg PO BID.
- Patients with a Baseline platelet count of 50,000/ μ L – <100,000/ μ L / μ L will begin dosing at 5 mg BID (one 5 mg tablet BID)
- Patients with platelet counts less than 50,000/ μ L are ineligible for the study (see [Section 5.2](#) and [Section 5.3](#)).

Dosage Tablet Combinations for Patients

For 25 mg PO BID	For 20 mg PO BID	For 15 mg PO BID	For 10 mg PO BID	For 5 mg PO BID
Two 10 mg tablets	Four 5 mg tablets	One 10 mg tablet and	One 10 mg tablet	One 5 mg tablet

For 25 mg PO BID	For 20 mg PO BID	For 15 mg PO BID	For 10 mg PO BID	For 5 mg PO BID
and one 5mg tablet		one 5 mg tablet		
One 10 mg tablet and three 5 mg tablets	Two 10 mg tablets	Three 5mg tablets	Two 5 mg tablets	
Five 5 mg tablets	Two 5 mg tablets and one 10 mg tablet			

INC424 tablets will be administered orally without regards to food in an outpatient setting in accordance with the specified dosing schedules. The dosage strength is 5 mg or 10 mg per tablet INC424. INC424 tablets are to be taken orally BID, approximately 12 hours apart (morning and night). INC424 will be self-administered by the patient, and each investigator should instruct the patient to take the study drug as per protocol (if applicable). All dosages prescribed and dispensed to the patient and all dose changes during the study must be recorded on the Dosage Administration Record (DAR) eCRF.

A standardized approach is to be taken for dosing adjustments and for safety and efficacy so that each patient is titrated to their most appropriate doses (see [Section 6.2](#)). Doses of INC424 are not to exceed 25 mg PO BID

Table 6-1 Dose and treatment schedule

Study drugs	Pharmaceutical form and route of administration	Dose	Frequency
INC424	Tablet for oral use	See Section 6.1.1 .	BID continuously

6.2 Dose modifications

6.2.1 Dose increases of INC424

6.2.1.1 Dose modification for patients starting INC424 at a dose of 15 – 20 mg BID

[figure not shown]
6.2.1.1.1 Dose increases of INC424 at week 4

As indicated in [Section 6.1.1](#) Study Drug Dosing, the initial dose of INC424 will be determined by the Baseline platelet count. In order to optimize each patient's dosage, after the first 4 weeks of therapy, doses may be increased by 5 mg BID for patients who meet all of the following conditions:

- Palpable spleen length below the costal margin that has been reduced by LESS THAN 40% at Week 4 visit relative to Baseline.
- Platelet count at the Week 4 blood draw is $> 150,000/\mu\text{L}$ and platelet count has never been below $150,000/\mu\text{L}$ at a prior laboratory evaluation while receiving INC424. (See [Figure 6-1](#)).

Absolute neutrophil count (ANC) levels have remained at or above $1000/\mu\text{L}$ since enrollment in the study.

Figure 6-1 Dose increase strategies for patients starting on INC424 15 – 20 mg BID with inadequate responses after at least Week 4:

6.2.1.1.2 Dose increases beyond week 4

After Week 4 (month 1), dose increases of INC424 are allowed for those patients who exhibit an INCREASE in palpable spleen length. The rules for these optional dose increases are as follows:

- The dose increases may only occur if the platelet count and ANC data for that visit are available.
- The palpable spleen length for that Study Visit must show a 2 cm or greater INCREASE in length compared to the on-study nadir (lowest palpable spleen measurement during the study, including Baseline).
- The patient must NOT have had a prior safety-related dose reduction.
- The following platelet threshold have been met:
 - The patient must have had a platelet count $\geq 150,000/\mu\text{L}$ at every assessment since Baseline for those starting INC424 at a starting dose of 15 – 20 mg BID.
 - The patient must have had ANC $\geq 1000/\mu\text{L}$ at every assessment since baseline.
 - The dose increase may only be an increase of 5 mg BID.
 - The total dose may never exceed 25 mg BID.
 - Following a dose increase, platelet count and ANC levels should be assessed approximately 2 weeks after the dose adjustment. If a regularly scheduled Study Visit does not coincide with this required blood draw, an unscheduled Interim Visit should be held to collect samples for hematology.

Dose adjustments for safety (Section 6.2.2), and reinstatement of doses (Section 6.2.3) will apply whether the patient is on the original dose, or a dose that was increased for lack of efficacy.

6.2.1.2 Dose modification for patients starting INC424 at a dose of 5 mg BID

6.2.1.2.1 Dose increases at week 4

For those patients who start INC424 treatment at a dose of 5 mg BID, dose increases can be made as described below. The dose can be escalated 5 mg once a day starting at week 4, and thereafter no more than every two weeks ONLY if:

- Inadequate efficacy is seen with the current dose level (See [Section 6.2.1.1.1](#))
- No treatment-related toxicity has occurred with the current dose level, resulting in treatment reduction or interruption or discontinuation in the previous 28 days
- The minimum platelet count at the time of the escalation is $\geq 50,000/\mu\text{L}$
- ANC $> 1000/\mu\text{L}$ since last scheduled visit
- The total dose may never exceed 25 mg BID

[figure not shown]
If the above criteria are met, then the INC424 dose can be increased by 5 mg o.d. e.g., from 5 mg BID to 5 mg QAM and 10 mg QPM.

6.2.1.2.2 Dose increases beyond week 4

After Week 4, dose increases of INC424 are allowed for those patients who exhibit an INCREASE in palpable spleen length. The rules for these optional dose increases are as follows:

- The dose increases may only occur if the platelet count and ANC data for that visit are available.
- The palpable spleen length for that Study Visit must show a 2 cm or greater INCREASE in length compared to the on-study nadir (lowest palpable spleen measurement during the study, including Baseline).
- The patient must NOT have had a prior safety-related dose reduction.
- The following platelet threshold have been met:
 - The patient must have had a platelet count $\geq 50,000/\mu\text{L}$ at every assessment since Baseline for those starting INC424 at a starting dose of 5 mg BID
- The patient must have had ANC $\geq 1000/\mu\text{L}$ at every assessment since baseline.
- The dose increase may only be an increase of 5 mg once daily for those starting on an INC424 dose of 5 mg BID.
- The total dose may never exceed 25 mg BID.
- Following a dose increase, platelet count and ANC levels should be assessed approximately 2 weeks after the dose adjustment. If a regularly scheduled Study Visit does not coincide with this required blood draw, an unscheduled Interim Visit should be held to collect samples for hematology.

Dose adjustments for safety ([Section 6.2.2](#)), and reinstitution of doses ([Section 6.2.3](#)) will apply whether the patient is on the original dose, or a dose that was increased for lack of efficacy.

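### For 5 mg BID starters, Protocol 6.2.1.2.1, 6.2.1.2.2 and the synopsis overlap after Week 4 and set different conditions for the same optional dose increase, and no text says which prevails

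*Protocol*

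**What the plan says.** Protocol 6.2.1.2 governs dose increases for patients who start at 5 mg BID. Its first subsection, 6.2.1.2.1, is headed as applying at Week 4, but the sentence that introduces its conditions is "The dose can be escalated 5 mg once a day starting at week 4, and thereafter no more than every two weeks ONLY if", and it closes with "If the above criteria are met, then the INC424 dose can be increased by 5 mg o.d". The second subsection, 6.2.1.2.2, is headed as applying beyond Week 4 and opens "After Week 4, dose increases of INC424 are allowed for those patients who exhibit an INCREASE in palpable spleen length". The synopsis (row on dose, regimen and treatment) introduces its own list for this cohort with the same sentence as 6.2.1.2.1. All three concern the same step of 5 mg once daily under the same ceiling. Their conditions are:

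| Condition | 6.2.1.2.1 | 6.2.1.2.2 | Synopsis |
|---|---|---|---|
| Spleen trigger | Inadequate efficacy, by reference to 6.2.1.1.1, where the criterion is "Palpable spleen length below the costal margin that has been reduced by LESS THAN 40% at Week 4 visit relative to Baseline" | Length "must show a 2 cm or greater INCREASE in length compared to the on-study nadir" | None listed |
| Safety history | No treatment-related toxicity at the current dose level "resulting in treatment reduction or interruption or discontinuation in the previous 28 days" | "The patient must NOT have had a prior safety-related dose reduction" | No earlier safety-related reduction, and no safety-related reduction or interruption after the last planned visit |
| Platelets at least 50,000/µL | When the dose is escalated | At each assessment back to Baseline | Since the last scheduled laboratory visit |
| ANC | Above 1000/µL "since last scheduled visit" | 1000/µL or more at each assessment back to Baseline | Above 1000/µL since the last scheduled visit |

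**The concern.** The two subsections look as if they divide the time axis at Week 4, but the wording of the first, repeated in the synopsis, carries it into the period of the second. After Week 4, three different lists then bear on one discretionary increase, and the text gives no order of precedence.

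The patients concerned are those with baseline platelets from 50,000 to below 100,000/µL, the group that Protocol 11.7 singles out for an interim look at risk and benefit. Protocol 6.1.1 calls for a standardized approach to dose adjustment. Protocol 12.2 and 12.10 permit no authorized deviations and require significant ones to be reported in the study report. If the rule depends on which page a site reads, both the conduct and the deviation count become hard to interpret.

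**Working it through.** There is no planned figure to reproduce. The check applies the three lists to hypothetical 5 mg BID starters after Week 4. Spleen lengths and counts are assumed; visit days come from Protocol Table 7-1 (Week 8 = Day 56, Week 12 = Day 84, Week 24 = Day 168).

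**Step 1. Synopsis against 6.2.1.2.2, leaving 6.2.1.2.1 aside.** Patient at Week 24: spleen 15 cm at Baseline, nadir 12 cm, now 14 cm; no safety-related reduction or interruption; platelets at least 50,000/µL throughout; ANC 900/µL at Week 8 and above 1000/µL at every other assessment.

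- Regrowth over nadir: 14 − 12 = 2 cm, so the spleen trigger of 6.2.1.2.2 is met.
- Change from Baseline: (14 − 15)/15 = −6.7%.
- 6.2.1.2.2: the lowest ANC since Baseline is 900, below 1000, so the increase is barred on this condition alone.
- Synopsis: the last scheduled visit before Week 24 is Week 12, and ANC has been above 1000/µL since then. All its listed conditions are met.
- An ANC of 900/µL does not itself require a dose change in this cohort: the synopsis and 6.2.3.2 call for a hold below 500/µL. The bar on prior reductions therefore does not remove the case.

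**Step 2. Control.** Change only the Week 8 value, so that ANC is above 1000/µL throughout. The patient now meets both 6.2.1.2.2 and the synopsis. The count window alone caused the difference.

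**Step 3. The reverse direction.** Spleen 20 cm at Baseline, nadir 14 cm, now 16 cm (regrowth 16 − 14 = 2 cm), clean safety history, adequate platelets, lowest ANC since Baseline and since the last visit both exactly 1000/µL. 6.2.1.2.2 is met because it accepts 1000. The synopsis and 6.2.1.2.1 fail because they require more than 1000. So 6.2.1.2.2 is not simply the stricter list.

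**Step 4. Can one patient satisfy all three?** Take the Step 3 spleen values with ANC 2000/µL. Change from Baseline is (16 − 20)/20 = −20%. With the 40% criterion read forward from Week 4, all three lists are met, so they are not mutually exclusive.

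**Step 5. 6.2.1.2.1 after Week 4.** In Step 1 its ANC, platelet and toxicity conditions are met. Its efficacy condition cannot be settled from the text, because the criterion it refers to is written for the Week 4 visit. If carried forward, 6.7% is less than 40% and the condition is met; if not, 6.2.1.2.1 has no defined trigger after Week 4.

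**Step 6. Safety look-back, as an isolated condition.** A safety-related reduction at Week 8 is 168 − 56 = 112 days old at Week 24. That is outside the 28-day look-back of 6.2.1.2.1 but still fails 6.2.1.2.2 and the synopsis. This shows only how that condition differs: 6.2.1.2.1 is further limited to the current dose level, and such a patient may fall under the reinstitution rule in 6.2.3.2.

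**The case against.** The strongest reply is that the headings separate the periods. They mirror 6.2.1.1.1 and 6.2.1.1.2 for the higher starting doses, and Protocol 7.5 and 7.5.1.3 place the first increase at the Week 4 visit. The two-weekly limit could be read as minimum spacing for later increases whose conditions then come from 6.2.1.2.2. This is a fair reading and may be what was intended, but the text does not state it, and it leaves the conflict between the synopsis and 6.2.1.2.2 (Step 1) in place.

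A second reply is that the synopsis is an abbreviation and states necessary conditions only. That may explain its missing spleen trigger, since it also omits the 2 cm condition for 15–20 mg starters. It does not explain the count windows. For later increases in 15–20 mg starters the synopsis repeats the body's window back to Baseline; for 5 mg starters it gives a different one.

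A third reply is that a site can satisfy every list at once. A reader might infer from the differences that the lists cannot be applied together. The documents do not support that: Step 4 is a patient who meets all three, and a permission in one list need not override a prohibition in another. What stands is that no sentence requires joint application.

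A reader might also infer that 6.2.1.2.1 plainly allows an increase at, say, Week 12 for a 20% spleen reduction without regrowth. That depends on carrying the Week 4 criterion forward, which the text leaves open.

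**Conclusion.** The point holds as an internal inconsistency in the current protocol text. After Week 4 the same optional 5 mg once-daily increase can conform to one passage and deviate from another. The firm part is the disagreement between the synopsis and 6.2.1.2.2, which runs in both directions (Steps 1 and 3) and needs no assumption about 6.2.1.2.1. The overlap of 6.2.1.2.1 with 6.2.1.2.2 is a real ambiguity of scope, but its practical result depends on the unstated reach of the Week 4 criterion.

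The size is limited. The cases are hypothetical, and the documents do not allow the number of affected patients to be derived. It would be wrong to infer an effect on the analysis sets or tests: the Per Protocol exclusions in SAP 2.1 are age, unconfirmed diagnosis and fibrosis grade, and the analyses are descriptive.

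A reader might infer a further contradiction from Protocol 6.2.2, where the hold below 50,000/µL carries no cohort label while Table 6-3 prescribes a reduction between 25,000 and 50,000/µL for 5 mg starters. The synopsis and 6.2.6 confine that hold to 15–20 mg starters, so this is mainly a missing label. Likewise, 6.2.3.2 not saying where reinstitution ends is a drafting gap, not a contradiction.

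**What to change.** Reconcile 6.2.1.2.1, 6.2.1.2.2 and the synopsis into one rule set for 5 mg BID starters with a stated time scope. It should say whether the Week 4 spleen criterion applies after Week 4, and use one safety-history condition and one count window, with the ANC inequality written the same way throughout. The clinical team chooses the rule; none is proposed here.

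As minor alignment, reconcile the cohort scope of the hold sentence in 6.2.2 with the synopsis and 6.2.6. Also reconcile the wording of the lowest allowed dose in 6.2.6 and 7.6.1 with Table 6-3: 7.6.1 adds low-platelet patients, and one Table 6-3 step from 5 mg BID gives 10 − 5 = 5 mg per day.

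The cost is a protocol clarification or amendment and a letter to sites with patients still on treatment. Protocol 4.1 plans the last visit for December 2016, but the documents do not show how many patients remain. Data collection and analysis do not change.
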